### **2.1.6. Diagnostic laboratory tests**

#### **A. Specimens, Microscopic Examination, and Culture**

Specimens include cerebrospinal fluid, tissue, exudates, sputum, blood, cutaneous scrapings, and urine. Spinal fluid is centrifuged before microscopic examination and culture. For direct microscopy, specimens are often examined in wet mounts, both directly and after mixing with India ink, which delineates the capsule. Colonies develop within a few days on most media at room temperature or 37°C. Media with cycloheximide inhibit *Cryptococcus* and should be avoided. Cultures can be identified by growth at 37°C and detection of urease. Alternatively, on an appropriate diphenolic substrate, the phenol oxidase (or laccase) of *C. neoformans* and *C. gattii* produces melanin in the cell walls and colonies develop a brown pigment.

#### **B. Serology**

Tests for capsular antigen can be performed on cerebrospinal fluid, serum and urine. The latex slide agglutination test or enzyme immunoassay for cryptococcal antigen is positive in 90% of patients with cryptococcal meningitis. With effective treatment, the antigen titer drops—except in AIDS patients, who often maintain high antigen titers for long periods (Brooks et al., 2013).

### **2.1.7. Complications**

Complications are common; raised intracranial pressure in the absence of ventricular dilatation may cause profound visual or hearing loss. Less commonly, patients may develop cognitive impairment and gait ataxia due to obstructive hydrocephalus with ventricular dilatation (Bicanic & Harrison, 2005).

#### **(a) Raised intracranial pressure**

The pathophysiology of elevated ICP in patients with cryptococcal meningitis is poorly understood and it is likely caused by several convergent factors. It has been postulated that it may be due to the outflow obstruction precipitated by aggregation of fungal polysaccharide accumulating in arachnoid villi and subarachnoid spaces thus providing the blockage of the channels for CSF drainage (Lee et al., 1996). Moreover, another possible important factor is cerebral oedema resulting from cytokine-induced inflammation and possibly osmotic effect by fungus-derived mannitol (Denning et al., 1991).

#### **(b) Ophthalmologic Complications**

The most severe ophthalmologic complication of cryptococcal meningitis is optic atrophy with resultant marked diminution of vision. This atrophy appears, at least in some patients, to be the result of direct invasion and destruction of the optic nerve by the cryptococci. The patients with most severe visual loss either had optic atrophy when first seen, or presented with minimal papilledema in relationship to CSF pressure (Okun & Butler, 1964).

## 2.1.8. Induction, consolidation and maintenance antifungal treatment regimens

Table 1. WHO 2018 Induction, consolidation and maintenance antifungal treatment regimens (WHO, 2018)

Induction (adults, adolescents and children)		
Preferred regimen	amphotericin B deoxycholate (1.0 mg/kg/day) and flucytosine (100 mg/kg/day, divided into four doses per day) (one week), followed by 1 week of fluconazole (1200 mg/day for adults, 12 mg/kg/day for children and adolescents, up to a maximum dose of 800mg daily)	Strong recommendation, moderate certainty evidence for adults, low-certainty evidence for children and adolescents
Alternative	Two weeks of fluconazole (1200 mg daily for adults, 12 mg/kg/day for children and adolescents) + flucytosine (100 mg/kg/day, divided into four doses per day)	strong recommendation, moderate-certainty evidence
Alternative	Two weeks of amphotericin B deoxycholate (1.0 mg/kg/day) + fluconazole (1200 mg daily for adults, 12 mg/kg/day for children and adolescents up to a maximum of 800 mg daily)	strong recommendation, moderate-certainty evidence
Consolidation		
Consolidation	Fluconazole (800 mg daily for adults, 6–12 mg/kg/day for children and adolescents up to a maximum of 800 mg daily) for eight weeks following the induction phase	strong recommendation, low-certainty evidence
Maintenance (or secondary prophylaxis)		
Maintenance (or secondary prophylaxis)	Fluconazole (200 mg daily for adults, 6 mg/kg/day for adolescents and children)	strong recommendation, high-certainty evidence

In March 2018, WHO published “Guidelines for the Diagnosis, Prevention and Management of Cryptococcal Disease in HIV-Infected Adults, Adolescents and Children”. This guideline recommends a short-course (one-week)

induction regimen with amphotericin B deoxycholate and flucytosine followed by 1 week of fluconazole is the preferred regimen. In low- and middle-income countries, due to limited availability of flucytosine, alternative options of two weeks amphotericin B deoxycholate plus fluconazole are used depending on drug availability (WHO, 2018). Although guidelines exist for the antifungal management of cryptococcal meningitis, recommendations are based on limited data from RCTs, and in clinical practice treatment is highly variable due to drug costs, availability, and ability to monitor and manage drug-related toxicities (Perfect, 2010).

Table 2. Myanmar Specialist hospital guidelines for clinical management of Cryptococcosis in patients with HIV (2019)

Initiation	IV Amphotericin 1 mg/kg plus Fluconazole 1200 mg IV/oral/ day for at least 2 weeks
Consolidation	Fluconazole 800 mg po od for 8 weeks
Maintenance	Fluconazole 200 mg OD until CD4 count rises to 200/mm  with ART

#### Treatment for localized non-meningeal disease

Treatment with fluconazole 800 mg/day for two weeks followed by 400 mg/day for eight weeks followed by fluconazole 200-mg/day maintenance therapy is suggested based on expert opinion.

For optimal treatment of cryptococcoma, the following treatment regimen is suggested based on expert opinion: intravenous amphotericin B and oral flucytosine for at least six weeks, followed by consolidation and maintenance therapy with fluconazole (all doses similar to those used for cryptococcal meningitis). Corticosteroids or surgical intervention may be considered for intracranial lesions with evidence of mass effect (WHO, 2018).

#### Treatment for pregnant women

Amphotericin B therapy can be given to pregnant women with meningeal and non-meningeal disease. Exposure to flucytosine and fluconazole during pregnancy has been associated with an increased risk of birth defects in animal studies and some uncontrolled human studies. The use of flucytosine and fluconazole for treating cryptococcal disease in pregnant women should be evaluated on an individual basis, considering the benefits and potential harm (WHO, 2018).

### **2.1.9. Adjunctive corticosteroids in treating HIV-associated cryptococcal meningitis**

Routine use of adjunctive corticosteroid therapy during the induction phase is not recommended in treating HIV-associated cryptococcal meningitis among adults, adolescents and children (strong recommendation, high-certainty evidence for adults and adolescents, moderate-certainty evidence for children) (WHO, 2018).

### **2.1.10. CSF fungal clearance**

Thailand study revealed that clearance of Cryptococci from the CSF was exponential and was significantly faster with amphotericin B plus flucytosine than with amphotericin B alone ( $p=0.0006$ ), amphotericin B plus fluconazole ( $p=0.02$ ) (Brouwer *et al.*, 2004). In Vietnam study, amphotericin B plus flucytosine was associated with significantly increased rates of yeast clearance from cerebrospinal fluid ( $-0.42 \log_{10}$  colony-forming units [CFU] per milliliter per day vs.  $-0.31$  and  $-0.32 \log_{10}$  CFU per milliliter per day in groups 1 (amphotericin B) and 3 (Amphotericin B plus fluconazole), respectively;  $P<0.001$  for both comparisons (Day *et al.*, 2013). Largest ACTA trial confirmed that flucytosine as the partner drug given with amphotericin B was associated with more rapid clearance than fluconazole (Molloy *et al.*, 2018).

### **2.1.11. Preventing, monitoring and managing antifungal toxicity**

#### Preventing, monitoring and managing antifungal amphotericin B toxicity

Drug toxicity and side-effects from amphotericin B therapy, especially hypokalaemia, nephrotoxicity and anaemia, are barriers to optimal induction treatment, safe administration of amphotericin B should be given priority and may require referral to a centre with access to a minimum package of preventing, monitoring and managing toxicity (WHO, 2018).

Table 3. Minimum package for preventing, monitoring and managing amphotericin B toxicity (WHO, 2018).

Pre-emptive hydration and electrolyte supplementation	
Adults and adolescents	One litre of normal saline solution with 20 mEq of potassium chloride (KCl) over two hours before each controlled infusion of amphotericin B and one to two 8-mEq KCl tablets orally twice daily. An additional 8-mEq KCl tablet twice daily may

	be added during the second week. If available, magnesium supplementation should also be provided (two 250-mg tablets of magnesium trisilicate or glycerophosphate twice daily, or magnesium chloride 4 mEq twice daily).
Monitoring (adults, adolescents and children)	
Serum potassium	Baseline and 2–3 times weekly (especially in the second week of amphotericin B administration)
Serum creatinine	Baseline and 2–3 times weekly (especially in the second week of amphotericin B administration)
Haemoglobin	Baseline and weekly
Management (adults, adolescents and children)	
Hypokalaemia	If hypokalaemia is significant ( $K <3.3$ mol/l), increase potassium supplementation to 40 mEq KCl by intravenous infusion and/or one to two 8-mEq KCl tablets orally three times daily. Monitor potassium daily.
Elevated creatinine	If creatinine increases by $\geq 2$ fold from the baseline value, increase pre-hydration to 1 L every eight hours and consider temporarily omitting a dose of amphotericin B. Once creatinine improves, restart amphotericin B at 0.7 mg/ kg/day and consider alternate-day amphotericin B. If creatinine continues to rise, consider discontinuing amphotericin B and continuing with fluconazole at 1200 mg/ day, especially if seven doses of amphotericin have been received. Consider fluconazole dose adjustment if significant renal impairment. Monitor creatinine daily.
Severe anaemia	Transfusion should be undertaken if possible for severe amphotericin B–related anaemia (anaemia may also be a reason to discontinue amphotericin B prematurely in the second week of a planned two-week induction course of amphotericin B with fluconazole)
Additional notes:	

- Potassium replacement should not be given to people with pre-existing renal impairment or hyperkalaemia.
- Careful attention should be given to monitoring of intake and output of fluid and daily weight, especially among children.
- Flucytosine – because of concerns about bone marrow suppression, regular monitoring of full blood counts should be considered.
- The incidence of renal dysfunction and electrolyte disturbance is much less with liposomal amphotericin preparations, but renal function and electrolytes still need to be monitored

### Managing fluconazole toxicity

#### -Renal insufficiency

If renal function decreases to 20-50 ml/min then reduce the dose by 50%

If renal function decreases to < 20 ml/min then reduce the dose by 25%

#### -Liver function abnormality (Perfect et al., 1992)

If during therapy, ALT (SGPT) from normal to 5x upper limit or form abnormal baseline increases by 150 then, if possible, stop fluconazole and switch to amphotericin.

#### -Drug Interactions

Fluconazole may increase levels of phenytoin, warfarin and sulfonylurea derivatives. If concomitant use of warfarin: check INR. If concomitant use of sulfonylurea derivatives there is risk of hypoglycemia, so check glucose levels more often.

Rifampicin will reduce the levels of fluconazole if the patient has been on it for > 2 weeks. Increase the dose of fluconazole by 50 %, in consolidation and maintenance phases.

Fluconazole is contraindicated in combination with cisapride and the new drug class of antihistamines such as terfenadine and astemizole (Molloy et al., 2018).

### **2.1.12. Safety**

In ACTA trial, they randomly assigned HIV-infected adults with cryptococcal meningitis to receive an oral regimen (fluconazole [1200 mg per day] plus

flucytosine [100 mg per kilogram of body weight per day] for 2 weeks), 1 week of amphotericin B (1 mg per kilogram per day), or 2 weeks of amphotericin B (1 mg per kilogram per day). Each patient assigned to receive amphotericin B was also randomly assigned to receive fluconazole or flucytosine as a partner drug. Laboratory-defined side effects were less frequent in the oral-regimen group than in the 1-week or 2-week amphotericin B groups. Grade 4 anemia developed in 0.9% of patients in the oral-regimen group, 4.9% of patients in 1-week amphotericin B groups, and 8.8% of patients in the 2-week amphotericin B group. And also Grade 3 anemia developed in 4% of patients in the oral-regimen group, 8.9% of patients in 1-week amphotericin B groups, and 17.5% of patients in the 2-week amphotericin B group. A grade 3 or 4 increase in the serum creatinine level developed in 4.9% of patients in the oral-regimen group, 6.2% of patients in the 1-week amphotericin B groups, and 8.8% of patients in the 2-week amphotericin B groups. Grade 4 hypokalemia developed in only one patient, most likely because preemptive electrolyte replacement was provided for patients receiving amphotericin B.

Grade 4 neutropenia was recorded in 3.2% of the patients who were taking a regimen that included 2 weeks of flucytosine, in 0.9% of those taking 1 week of flucytosine, and in 1.3% of those taking a flucytosine free regimen. A grade 4 increase in the alanine aminotransferase level developed in only two patients, one of whom was taking fluconazole. Clinical adverse events were frequent with all regimens, which was reflective of the severe immunosuppression in this patient population.

As a partner drug with amphotericin, 1week amphotericin and flucytosine group develop Grade 3 and 4 anaemia of 8.8% and 24.56 % in 2 weeks amphotericin and fluconazole group. (Molloy et al., 2018).

In Vietnam trial, Grade 3 and 4 anaemia were most prominent between amphotericin B plus flucytosine (35%) and amphotericin B plus fluconazole group (29%). Grade 3 and 4 Neutropenia (9%) were similar between the two groups. 4% of amphotericin B plus flucytosine group develop Grade 3 and 4 thrombocytopenia with 3% in the fluconazole group. Grades 3 and 4 increase in aminotransferase level was 6% in flucytosine group and 14 % in fluconazole group (Day et al., 2013).

But in one cohort study of amphotericin B with fluconazole, none of the patients developed any serious Grade 3, 4 anaemia and elevated ALT level. Only 2 patients developed grade III hypokalemia and thrombocytopenia. And 7 patients

develop grade 3,4 neutropenia and 4 patients develop grade III elevated creatinine level. (Muzoora et al., 2011).

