#### **4.8. Materials and Methods**

After getting approval from medical superintendent, patients with HIV-associated cryptococcal meningitis admitted to inpatient departments of SHW, SHM and SHT will be studied. They will be given IV infusion of amphotericin B (1 mg/kg/day) and oral flucytosine (100 mg/kg) for one week followed by oral fluconazole (1200 mg/day) for one week according to the hospital standard treatment guideline chosen by the physician depends on patient's clinical condition. Before giving treatment, informed consent will be obtained.

All patients meeting the inclusion criteria will be studied under the supervision of experienced physicians. Baseline data for assessing clinical effectiveness such as fever, convulsion and abnormal mental status and for safety such as hematological and biochemical parameters (hemoglobin, neutrophil, platelet, ALT, AST, serum creatinine and serum potassium level) will be noted from medical charts. Hematological and biochemical parameters will be graded according to DAIDS grading. Assessment of headache and its severity will be done by numerical rating scale under the supervision of physician.

Seven days and fourteen days after treatment, clinical effectiveness parameters such as headache, fever, convulsion, abnormal mental status and death will be reassessed. Clinical safety concerning hematological and biochemical parameters like hemoglobin, neutrophil, platelet, ALT, AST, serum creatinine and serum potassium level will also be reassessed and graded according to DAIDS grading by reviewing from patient's medical charts at seven and fourteen days. With regard to severity of headache, it will be documented by using numerical rating scale at weekly intervals for two weeks. Clinical effectiveness parameters (headache, fever, convulsion, abnormal mental status and death) and hematological and biochemical parameters will be described. The results will be documented for data analysis.

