#### **4.11. Ethical Considerations**

The study will be hospital-based descriptive study regarding the clinical effectiveness and safety of amphotericin B with flucytosine-fluconazole combination therapy for treatment of HIV-associated cryptococcal meningitis. In this study, all patients according to selection criteria admitted to inpatient departments of SHW, SHM and SHT will be included. The participants eligible to the selection criteria will be invited to voluntary participation in the study and then explained in details about the study by the investigator with the information sheet of informed consent form (Part-I).

Only after they have understood the nature of study, objectives, methodology, procedure and duration, they can voluntarily take part in the study or they have right to refuse or withdraw at any time from the study without penalty of loss of benefit to which he or she would otherwise be entitled. If they agree, the written informed consent will be obtained by using informed consent form (Part-II) from all participants or from parents/relatives/next of kin if the patient could not provide the consent.

[figure not shown]
The study will be done under the supervision of a physician. The study will collect data under routine management. No new drugs will be administered and no treatment will be restricted for the purpose of thesis. The participants will be closely monitored throughout the research process. If any adverse reactions occur, the researcher will immediately inform to the physician and urgent treatment will be given and the necessary actions will be taken according to the standard treatment procedure.

The investigator will strictly maintain the rules of privacy and confidentiality. The name of patients will not be mentioned in this study. Only coded system will be used and research information will be kept by a password-protected file in the investigator's personal computer. All the personal information of the subject in Pro forma will be destroyed and the personal information in the investigator's personal computer will be deleted after the study period. The presentation on research data will be used in medical workshop, seminars and conference and the data will also be published for the academic purposes- only in thesis, papers and medical journals if necessary.

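### Transfusion is not recorded, so grade 3/4 anaemia, the outcome that sizes the safety part, can be missed between the three haemoglobin draws

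*Combined protocol and SAP*

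**What the plan says.** **Sizing.** Section 4.7.1 takes the absence of grade III/IV anaemia as the safety proportion, with p = 0.83, absolute precision 0.14 and n = 27.

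**Data capture.** Section 4.8 and pro forma section X (Annex 1) take seven laboratory values, haemoglobin among them, at baseline, day 7 and day 14. Pro forma section V lists amphotericin B, flucytosine and fluconazole and nothing else. No field on the form records transfusion, pre-hydration, potassium or magnesium. Section III does record the volume of therapeutic lumbar puncture, which is a supportive procedure.

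**Reporting.** Section 4.9 plans numbers and percentages. Table 10 reports grade 3 and 4 anaemia, neutropenia and thrombocytopenia by time point. Table 11 reports bone marrow suppression, which section 4.10 defines as grade 3 or 4 in at least one of those three. The title of Table 9 assigns the laboratory events to the three antifungals.

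**What the literature review says about supportive care.** On anaemia, Table 3 (section 2.1.11) says "Transfusion should be undertaken if possible for severe amphotericin" B-related anaemia. It also lists "One litre of normal saline solution with 20 mEq of potassium chloride (KCl) over two hours before each controlled infusion of amphotericin B" and, when creatinine at least doubles, "increase pre-hydration to 1 L every eight hours and consider temporarily omitting a dose of amphotericin B". Section 2.1.12 reports a single patient with grade 4 hypokalaemia in the African reference trial, "most likely because preemptive electrolyte replacement was provided for patients receiving amphotericin B".

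**What the study itself fixes.** Section 4.8 gives the antifungals "according to the hospital standard treatment guideline chosen by the physician depends on patient's clinical condition", and section 4.11 states: "The study will collect data under routine management".

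**The concern.** The safety part is sized on an outcome that a recorded haemoglobin can hide. A patient may fall to grade 3 or 4 on, say, day 4 or day 10, be transfused, and reach the next scheduled draw with a value above the grade 3 limit. The form then holds no trace of the event, and Table 10 counts the patient as not having grade 3/4 anaemia. If neutrophils and platelets stayed below grade 3 severity, the patient also drops out of Table 11.

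The error runs one way. It lowers the grade 3/4 anaemia percentage and raises the proportion free of it, so the regimen looks safer than it was. Section 1.2 says the study is meant to establish a safety profile for a regimen about to be supplied nationally, and anaemia is one of the two main toxicities of amphotericin B named in section 1.1.

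Pre-infusion saline, potassium and magnesium raise a lesser question of the same kind. Without a record of them, a reader of Table 9 cannot tell under what supportive care the potassium and creatinine percentages arose.

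**Working it through.** **1. The plan's own figure.** With n = z²p(1−p)/d² and z = 1.96:
- safety: 1.96² × 0.83 × 0.17 / 0.14² = 27.66
- effectiveness: 1.96² × 0.80 × 0.20 / 0.15² = 27.32

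Both would round up to 28. The stated 27 reproduces to within one patient, and the point does not turn on it.

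**2. Weight of one patient.** 1/27 = 3.7 percentage points, about a quarter of the stated precision (3.7/14 = 0.26). This takes all 27 as the denominator. Section 4.7.2 includes all admitted patients, so a larger enrolment would shrink the share. Deaths or missing draws would raise it.

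**3. Expected cases at the planning rate.** 1 − 0.83 = 0.17, and 27 × 0.17 = 4.6 patients with grade 3/4 anaemia.

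**4. Range of effect.** The documents give no transfusion rate, so the number masked is an assumption. Observed percentage = (4.59 − m)/27:

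| Patients masked (m) | Observed grade 3/4 anaemia |
|---|---|
| 0 | 17.0% |
| 1 | 13.3% |
| 2 | 9.6% |
| 3 | 5.9% |

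**5. When a transfused patient is masked.** In Annex 3, grade 3 runs up to 9.0 g/dL in men and 8.5 g/dL in women. Masking needs both of the following:
- the low value falls between scheduled draws;
- the next scheduled value lies above that limit.

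A patient raised only from grade 4 to grade 3 is still counted. A patient who is grade 3/4 at the day-7 draw and is then transfused is counted at day 7 but may leave the day-14 column. Not every transfusion therefore moves the result.

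**6. Table 11.** A masked patient is lost there only if neutropenia and thrombocytopenia are also below grade 3. The loss in Table 11 is therefore at most the loss in the anaemia row of Table 10.

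**7. Would splitting Table 9 by supportive care help?** Section 2.1.12 gives 6.2% grade 3/4 creatinine rise in the 1-week amphotericin B groups, and 27 × 0.062 = 1.7 expected patients. Dividing fewer than two events by package received says nothing. Table 3 also withholds potassium from people with pre-existing renal impairment and increases hydration because creatinine has risen, so the groups would differ by indication.

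**The case against.** The best defence is that this is a hospital-based descriptive study (section 4.1) under routine management. Objective 4 is to describe laboratory grades, and section 4.10 counts adverse events whatever their cause. On that footing the percentages are valid as a description of the regimen together with the care usually given. Leaving supportive care unfixed is what such a study does. The plan contains no comparison between hospitals (hospital appears only in Table 4, as enrolment) and none with other trials. The full hospital guideline is not reproduced, and the algorithm in section 4.12 cannot be read.

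Most of this stands. A reader might infer that the potassium, creatinine and haemoglobin percentages cannot be interpreted at all, or that the protocol is at fault for not standardising the package. The documents do not support either reading. The remark in section 2.1.12 concerns grade 4 hypokalaemia only and is hedged, and it does not explain the creatinine or anaemia results by supportive care. Table 3 is guideline text in the literature review, and the Methods do not adopt it.

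The defence does not reach transfusion. Counting events regardless of cause does not help if the event is never captured. Even as pure description, a table of grade 3/4 anaemia that omits patients corrected between draws is incomplete.

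Two further cautions are fair. Some transfusions will be for anaemia present before treatment or for other reasons, so the reason must be recorded. It is also not stated that the charts show support for each infusion, so a simple yes/no is all that should be asked there.

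**Conclusion.** The point holds for transfusion. With haemoglobin taken at three fixed times and transfusion unrecorded, Tables 10 and 11 can understate grade 3/4 anaemia and bone marrow suppression, and the proportion that sizes the safety part can be overstated. The size is 3.7 points per masked patient at n = 27. The total is unknown, because it depends on how many patients are transfused between draws and reach the next draw above the grade 3 limit. The percentages in the working for one to three masked patients show scale and are not estimates.

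For fluids, potassium and magnesium the conclusion is narrower. The gap is one of description: the Table 9 percentages are those seen under the regimen with routine supportive care, and the report should say so. A tempting further step is to call these rates confounded and to stratify them. The plan makes no comparison that would be confounded, and the expected counts are too small for a split.

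**What to change.** 1. **Pro forma section V:** add transfusion after the start of treatment (yes/no, date, units, reason, last haemoglobin before it), read from the charts already in use.
2. **Table 10:** next to the haemoglobin-only anaemia row, add a row for *grade 3/4 anaemia or transfused for anaemia after treatment start*. The gap between the two rows shows how far transfusion could have moved the result.
3. **Table 11:** give the same combined count as a sensitivity figure.
4. **Pre-infusion support:** record whether saline, potassium and magnesium were given (yes/no each), and report this descriptively by hospital beside Table 9. Do not split Table 9 by it.
5. **Table 9 wording:** describe the percentages as those observed under the regimen with routine supportive care.

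The cost is slightly longer chart abstraction and a combined anaemia figure that will look less favourable. The fields should be on the form before abstraction starts. Section 4.11 has personal information destroyed or deleted after the study period, which may prevent a later return to the charts. No change to patient care is proposed.
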